Study 1 Data Analysis Plan. A generalized linear model will be applied to examine fitting accuracy. This analysis will examine differences (in dB SPL) for in situ REAR (based on testbox fittings) across frequency between the groups relative to the prescription. Because it is expected that differences within the two ears of the same subject will be smaller than differences across subjects, inclusion of both ears in the same analysis may over inflate the statistical power. However, it is also of interest to ensure that all data are considered. Therefore, we propose to complete separate analyses for the left and right ear, even though we expect the pattern of results to be very similar for each ear. These analyses will determine (1) in situ REARs of the testbox fittings matched the prescription within each group, and (2) if there was an effect of fitting accuracy as a function of style. A generalized linear model will be conducted to compare the expected (from prescription) and actual aided SII within and between groups. Finally, separate mixed model repeated measures ANOVA will be applied to examine group differences among the outcome measure subscales (i.e., SADL subscales, IOI-HA items/subscales, and for the APHAB subscales) to examine differences in outcomes between groups and between current hearing aid fittings and the replacement testbox fittings. For the COSI, the percentage of 'better' and 'much better' responses and the average of the final ability will be calculated across goals and compared between groups via a paired-sample t-test. The subjective outcomes of replacement hearing aids (Session 3) from testbox fittings will also be compared to normative data for each group by comparing our mean, standard deviation, and sample size to those same variables from the published outcome respectively via a Welch test. This will inform whether our outcomes for testbox fittings of replacement hearing aids from each group were consistent with the published norms or not. For the IOI-HA, the IOI-HA norms from the VA ROES DALC database that contains over 100,000 IOI-HA records will be used. In the same fashion, we can select IOI-HA norms from ROES by based on degree of hearing loss and hearing aid style. A

logistic regression also will be conducted to examine if the proportion of responses differ between the groups on the specific telephone and exit survey items of interest.

Study 2 Power Analysis. The sample size for this aim is based on having 12 monaural hearing aid fittings (3 manufacturers of 1 open RIC, 1 closed RIC, 1 open RITA, and 1 closed RITA) per participant (ears counterbalanced across participants such that odd-numbered subjects obtain fittings in the left ear and even numbered in the right ear). To ensure a wide range of RECDs and the expected variability in slit leak venting with closed domes, our target sample size is now 96 participants. See randomization Table in Appendix 6 in the grant application for details. For this single session study, we will account for 10% attrition due screen failure and thus will recruit an additional 10 participants for a total of N = 106.

Study 2 Data Analysis. The data from this study will not be analyzed in the usual manner as the purpose of this study is to develop correction factors for open and closed dome fittings of RIC and RITA style hearing aids from several manufacturers. First the frequency-specific gain deviations for each ear as a function of vent size will be calculated. Second, Linear and nonlinear modeling of these data with the goal of developing a best fit model of the relationship between physical vent size and the frequency specific change in gain. The model will also be adjusted as a function of hearing loss, if necessary, to account for cases when the model correction would erroneously lead to negative gain.

Study 3 Power Analysis. A power analysis based on the same expectations as Study 1 regarding fitting accuracy was conducted. For a mixed model repeated measure ANOVA with an effect size $\eta^2 = 0.10$, power $(1-\beta) = 0.80$, and $\alpha = 0.05$ requires a sample size of 100 ears (total of 50 participants) over the four groups, or 13 participants per group. A small effect size is expected, as a small effect size was found in the SPIRE data ($\eta^2 = 0.10$). Nonetheless, considering increased variability due to venting and to obtain robustness required by clinical standards, we will increase the sample size to achieve higher power of $(1-\beta) = 0.95$. This would bring the sample size of ears to 152, or 76 participants in total (19 per group). Considering 15% attrition, then 12 additional participants will be needed (N = 88) resulting in 22 participants per group.

Study 3 Data Analysis. We will use a similar data analysis plan as in Study 1 for real ear/fitting accuracy variables. This will determine if derived REARs from open-fit RECD-fittings will accurately meet prescriptive targets and expected aided audibility and if *in situ* REARs of RECD-fittings are equivalent to *in situ* REARs in SoC fittings of open-fit styles. For statistical reasons, we propose to complete separate analyses for the left and right REAR data as described in Experiment 1. For self-report data, a separate mixed model repeated measures ANOVA will be conducted to compare outcomes amongst the groups. This will determine if subjective self-report outcomes across a variety of domains differs as a function of fitting experience and open-fit style.

The data will be analyzed by the PI; her collaborator and co-investigator ([name]., at Vanderbilt University—coded data only) who also will develop the correction factors; and the statistical consultant at Duke University (to be determined). A copy of coded data only will be

stored on the Duke University Server. A copy of all electronic data will also be stored at VA on \\v06.med.va.gov\\dur\\Research\\Research\\[name].

Privacy, Confidentiality, and Information Security

1. Lists of Data Reviewed and/or Collected for Screening/Recruitment and Conduction of Study:

It will be obtained, used, and/or shared for this study includes:

Identifier(s)	Source(s) of Health Information
 Names	 Medical history & physical exam information
 All geographic subdivisions smaller than a State, including street address, city, county, precinct, and zip code. Describe: mailing address	 Photographs, videotapes, audiotapes, or digital or other images
 All elements of dates (except year) for dates directly related to an individual, including birth date, admission date, discharge date, visit or treatment dates, etc.; and all ages over 89, Describe: age, audiology treatment dates (hearing test dates, fitting dates)	 Biologic specimens (e.g., blood, tissue, urine, saliva). Describe:
 Telephone numbers	 Progress notes
 Fax numbers	 Diagnostic / Laboratory test results
 Electronic mail addresses	 Operative reports
 Social Security Numbers	 Imaging (x-ray, CT, MRI, etc.)
 Medical record numbers	 Discharge summaries
 Health plan beneficiary numbers	 Survey / Questionnaire responses
 Account numbers	 Billing records
 Certificate and/or license numbers	 HIV testing or infection records
 Vehicle identifiers and serial numbers, including license plate numbers	 Sickle cell anemia information
 Device identifiers and serial numbers	 Alcoholism or alcohol use information
 Web Universal Resource Locators (URLs)	 Drug abuse information
 Internet Protocol (IP) address numbers	 Mental health (not psychotherapy) notes
 Biometric identifiers, including finger & voice prints	 Psychological test results
 Full-face photographic images and any comparable images	 Genetic testing
 Any other unique identifying number, linked study ID, characteristic, or code, describe: each substudy will have a unique study ID based on group assignment and number of subject entering the study. For example, Study 1: ITE01, BTE 01	 Other, describe:

2. Data and/or Specimen Acquisition:

Data for this study will be collected through (*check all that apply*):

- Prospective data and/or specimen collection obtained from participants. Provide description of processes: The prospective data will be collected from participants as described above for Study 1, Study 2, and Study 3.
- Retrospective data collection and/or specimens obtained from medical chart review/data access. Describe how data will be obtained (e.g., fileman, CDW, etc.): . Participant demographics (e.g., name, last 4 of social security number, age, gender, previous hearing-aid fitting date, and hearing aid information [make, model, style]), will be collected from CPRS. The prior audiogram and date will be collected from CPRS (Study 1 and 3) to ensure we meet the inclusion criteria.
- Retrospective data collection and/or specimens obtained from an IRB-approved data and/or specimen repository. Indicate the repository source including name, VA location, and IRB number: .

Note: for data and/or specimens obtained from a VA approved data repository, a Data Use Agreement (DUA) must be executed prior to obtaining data and/or specimens. See VHA Handbook 1200.12 for further information.

3. Level of Data:

The following level(s) of data will be acquired/maintained for this study (*check all that apply*):

- Identified (e.g., names, addresses or other identifiers included)
- Coded (direct and/or all identifiers removed, but study code/ID included)
- De-Identified (all HIPAA 18 and study ID/code removed):
 - Verified Statistically
 - OR
 - Verified by Absence or Removal of HIPAA 18 and study ID
- Limited Data Set
- Other: Describe: data will be de-identified to create a limited data set to be shared with other scientists as outlined in data management plan

4. Location of Data and/or Specimens, and Data Retention Plan:

A. Data and/or Specimen Location: Data will be stored electronically in \\v06.med.va.gov\\dur\\Research\\Research\\[name]. Data that will be stored electronically include the master study key that will store subject number, first name, last name, last 4 of SSN, consent date, and race/ethnicity. Coded data files will contain subject number, gender, age, fitting date, and all other variables related to the study procedures as listed above (primary hearing test, hearing aid data, and outcome data). A copy of the coded data file only (not master file with PHI) will be saved on a Duke University restricted folder only accessible by the study team (Please see attached approved ORD off-site waiver). For Study 1 and 3, the serial numbers of the hearing aids will be stored in the hearing aid fitting software on the Duke University server. The individual subject hearing aid fitting file will contain the subject code and fitting date, but the

serial numbers cannot be removed. The serial numbers of the hearing aids are also in the Veteran's CPRS record on the VA server and will not be stored in a data file.

Paper records of data include the consent document, HIPPA authorization, and coded participant folders and will be stored the MOSCH Duke lab (temporarily) and then at the Durham VAMC Audiology Clinic, Building #1, Room D3018 (permanently).

Electronic data will also be stored in the VA REDCap server. This would include any collected coded data including but not limited to hearing test data, hearing aid information, subject responses to questionnaires, surveys, or cognitive screeners. This data may initially be collected on paper forms and will then be input by study staff into the REDCap database. No PHI will be stored on the VA REDCap server.

VA REDCap is specifically designed for human subjects research. VA REDCap has the following features:

- Installed and accessible only on a VA network.
- Login requires VA Network ID.
- Housed on a VA Informatics and Computing Infrastructure (VINCI) server at the Austin Information Technology Center (AITC).
- Data is backed-up nightly and every 6 hours.
- Provides data de-identification features
- Captures audit trails and logging with individual user rights management
- Restricts access to Protected Health Information (PHI) at the user-level

Specimens are not collected as part of this research.

Data will be also be placed at the VA Informatics and Computing Interface (VINCI; <http://vaww.vinci.med.va.gov/vincicentral/VINCIWorkspace.aspx>). The VA Informatics and Computing Infrastructure is a partnership between the VA Office of Information Technology and the Veterans' Health Administration Office of Research and Development. Researchers and operations staff can use VINCI to access data and statistical analysis tools in a virtual working environment through a certified VHA network computer using the VA Intranet or Virtual Private Network (VPN).

B. Data Retention Plan

X Research records will be maintained and destroyed according to the National Archives and Records Administration, Records Schedule Number: DAA-0015-2015-0004. Records destruction, when authorized, will be accomplished using the then current requirements for the secure disposal of paper and electronic records. Currently, destruction of research records (see DAA-0015-2015-0004, section 7.6 "Research Investigator Files" for materials included in research records) is scheduled for 6 years after the cut-off (the cut-off is the completion of the research project) and may be retained longer if required by other federal agencies. Records will not be destroyed without pre-notification to the facility records manager.

Other data retention plan, describe:

Data Access and Data Recipients: Only members of the Durham VAMC study team will have access to the electronic master study key that will store identifiable information and be saved on the VA server. They also will have access to the participants' CPRS medical records stored on DVAMC servers. The electronic data files will only contain coded data with the direct identifies removed (e.g., name, address, phone number, SSN). The electronic coded data files will be stored on the VA server (\\v06.med.va.gov\dur\Research\Research\[name]) and a copy on a restricted Duke University folder (only accessible by the study staff) and shared via Azure with the Duke Department of Surgery statistical support staff member (statistician to be determined) who will facilitate the PI with data analysis. The electronic coded data file will also be shared via Azure with [name] (Vanderbilt University and Co-Investigator on the grant) who is responsible for the development of correction factors and other data analyses. Electronic coded data will also be stored in VA REDCap which is housed on a VINCI server at the Austin Information Technology Center (AITC). This data will only be accessible to study staff who have a VA Network ID login with VA REDCap.

VA research personnel who have access to VHA records are instructed, in accordance with VA policy, on the requirements of Federal privacy and information laws and regulations, VA regulations and policies, and VHA policy. All study personnel who are VA employees working within the VA system have fulfilled all required HIPAA and other VA security and privacy policy training requirements and have agreed to follow guidelines pertaining to the protection of patient data. All research staff sign VA Rules of Behavior, and all study staff are up-to-date with VHA Privacy Policy Training and the VA Office of Cyber and Information Security Awareness Training Course. The data security and privacy procedures summarized in that course include logging off or locking the computer when walking away from it; no sharing of access codes, verify codes or passwords; not allowing anyone else to use the computer under one's password; and disposing of sensitive information using VA-approved methods (e.g., shredder bins).

Access to study data will be removed for all study personnel when they are no longer part of the research team.

5. Data and/or Specimen Transportation and/or Transmission for all data and/or specimens involved in the study:

The data collection for all three sub-studies will occur at the MOSCH Lab at Hock Plaza at [name] (See approved off-site waiver from RR&D). The VA server will be accessed by the study team from this site remotely (VPN/CAG). Electronic data will be entered into data files via this method too. For participants who are consented at the Duke lab, their paper ICD and HIPAA authorization will be transported to DVAMC Audiology clinic. Coded paper data files will be transported to the DVAMC Audiology clinic when the data are entered electronically and participants are terminated from the study.

I. Data and/or specimens will not be transported or transmitted outside of Durham VAMC environment.

II. Data and/or specimens will be transported BETWEEN sites that are under the auspices of the Durham VA Medical Center.

III. Data and/or specimens will be transmitted to other VA sites using the following method(s):

A. Data

Data are de-identified and thus will be sent via unencrypted e-mail or unencrypted disk (encryption is optional).

Data are coded or contain identifiers and thus will be sent <choose method of transfer such as: PKI or RMS encrypted e-mail, FIPS 140-2 encrypted disk (with VA-authorized carrier and tracking), or FIPS 140-2 encrypted external drive (with VA-authorized carrier and tracking). You may identify a primary and secondary method>.

Other, describe:

B. Specimens

Specimens are de-identified and thus will be sent via standard carrier (tracking is optional).

Specimens are coded or contain identifiers and thus will be sent via VA-authorized carrier with tracking.

Other, describe:

IV. Data and/or specimens will be transported to non-VA/VHA sites (e.g., academic affiliates, laboratories, etc.) using the following method(s):

A. Data

Data are de-identified and thus will be sent via unencrypted e-mail or unencrypted CD.

Data are coded or contain identifiers and thus will be sent via <choose method of transfer such as FIPS 140-2 encrypted CD or FIPS 140-2 encrypted hard drive/flash drive> using VA—approved carrier with tracking.

Data are coded or identified and will be sent using Azure file encryption. [name]. Vanderbilt University and the statistician at Duke University (to be determined)

Data are coded or identified and will be uploaded to sponsor website using electronic case report form (eCRF) <insert information including sponsor name and URL and the encryption the site uses.>

Other, describe:

1. For participants consented at the MOSCH Duke lab, their original ICD and HIPAA authorization will be transported to DVAMC Audiology Clinic (Building 1, Room D3018) using a lockable VA envelope. Only the study staff will have access to the key. Coded paper participant data files will be transported to the DVAMC Audiology clinic in a locked VA envelope. Electronic coded data will be entered into the study files via a VPN/CAG connection. Electronic coded data will be shared with [name] and the Duke University statistician (TBD) for data analyses.

B. Specimens

Specimens are de-identified and thus will be sent via standard carrier (tracking is optional) or will be hand-delivered by research study personnel. Specify method of delivery:

Specimens are coded and thus will be sent via VA-approved carrier with tracking or will be hand-delivered by research study personnel. Specify method of delivery:

In accordance with the HIPAA and the Privacy Act, for any coded or identifiable data or specimens released from the Durham VAMC (with the exception of Limited Data Sets), an Accounting of Disclosure (AOD) will be maintained (e.g., in a database or spreadsheet) that includes the participant's name, date of the disclosure, description of the nature of the Individually Identifiable Information (III) disclosed, purpose of each disclosure, and the name and address of the person/agency to whom the disclosure was made.

C. Local DVAMC memorandum "Authorization to Use, Process, Store, or Transmit VA Sensitive Information Outside VA Owned or Managed Facilities" has been pre-filled out for each study team member who may transport the data and/or specimens off-site. This (these) forms are included with the IRB materials.

D. Containers (e.g., briefcase, bin) are labeled with the following notice (label placed on the outside of container) in accordance with VHA Directive 6609:

NOTICE!!!

Access to these records is limited to: AUTHORIZED PERSONS ONLY.
Information may not be disclosed from this file unless permitted by all applicable legal
authorities, which may include the Privacy Act; 38 U.S.C. §§ 5701, 5705, 7332; the
Health Insurance Portability and Accountability Act; and regulations implementing those
provisions, at 38 C.F.R. §§ 1.460 – 1.599 and 45 C.F.R. Parts 160 and 164. Anyone who
discloses information in violation of the above provisions may subject to civil and criminal
penalties.

- V. We will communicate with veterans enrolled as participants in this research study through MyHealtheVet.

6. Risk Mitigation Strategies:

Interactions with participants during consenting and data collection will occur by approved study staff members in a private location to ensure privacy of the participant.

Paper records that contain PHI or coded data will be kept in a locked cabinet in a locked office. During transport from Duke to VA, a locked VA envelope/suitcase labeled accordingly, will be used by approved study staff members only (after they sign the appropriate memo). Electronic data with PHI will be kept in a separate master file from the coded data to reduce the likelihood of identifying the participant. Unauthorized access will be mitigated by having key control over paper records and by restricted access to electronic folders to approved study staff only. The PI, study staff, collaborator, and statistical consultant will be responsible for overseeing the privacy of the participant and security of the data.

- Data are fully de-identified (stripped of HIPAA 18 and study ID/code) before being shared outside of Durham VAMC.
- Specimens are fully de-identified (stripped of HIPAA 18 and study ID/code before being shared outside of Durham VAMC.
- Direct identifiers will be maintained separately from data and or specimens by using a code to "identify" subjects. In a separate database (i.e., a "linking" or "cross-walk" database) this code will be linked to identifying subject information.
- Other, specify:

7. Suspected Loss of VA Information:

Should any incident such as theft or loss of data, unauthorized access of sensitive data or non-compliance with security controls occur it will be immediately reported according to VA policy. All incidents regarding information security/privacy incidents will be reported to the ISO and PO within 1 hour of acknowledgement of issue and done so using the VHADUR Research Events Report e-mail group ([contact]).

8. Reporting of Results:

- Reporting of results, such as in scientific papers and presentations, will never identify individual subjects. Data will be presented in aggregate and individual-level data will not be published.

- Other results reporting plan, describe:

9. Future Use of Data:

Data will be retained for future use. This is described elsewhere in the protocol and is noted in the HIPAA authorization.

Future Use of data is optional (i.e., not required by the research subject).

Future Use of data is required for participation in the study.

No future use of data is currently planned.

10. Use of Mail Merge Technology

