PROTOCOL TITLE: Efficacy of a Coupler-Based Fitting Approach for Experienced Users Receiving Replacement Hearing Aids

PRINCIPAL INVESTIGATOR: [name], Au.D., Ph.D.

VERSION NUMBER AND DATE: Version 10, June 10, 2022

SPONSOR/FUNDING SOURCE: VA RR&D Merit Review C2777-R

Purpose

The overarching purpose of this project is to develop an accurate coupler-based fitting model for experienced hearing-aid users obtaining replacement hearing aids of any style that will result in positive patient outcomes while mitigating a face-to-face fitting visit.

The proposed project addresses three aims:

Specific Aim 1. Develop vent correction factors for testbox fittings of in-the-ear (ITE) and traditional behind the ear (BTE) with custom earmold hearing aids, which will be used to evaluate the real ear to complete difference (RECD)-fitting approach in a sample of experienced users receiving replacement hearing aids. Hypothesis 1a. RECD coupler-based fittings will accurately meet prescriptive targets and expected aided audibility for ITE and traditional BTE styles. Hypothesis 1b. Subjective outcomes from RECD coupler-based fittings will meet or exceed published norms.

Specific Aim 2. Develop correction factors for RECD coupler-based fittings of hearing aids with non-custom coupling (i.e., mini-BTEs with slim tubing and noncustom open canal coupling—open fits). Hypothesis 2. Correction factors will be developed to account for RECD coupler-based fittings with open canals.

Specific Aim 3. To determine if the open-fit RECD-fitting approach is equivalent to the standard of care (SoC) open-fit fitting approach. Hypothesis 3a. Derived REARs from open-fit RECD-fittings will accurately meet prescriptive targets and expected aided audibility and will be equivalent to in situ REARs in SoC fittings of open-fit styles. Hypothesis 3b. The subjective outcomes will not significantly differ between the experimental RECD-fitting group and the SoC group for open-fit styles.

Background and Significance

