1c-Coupler-based fittings. Not all patients, however, can tolerate in situ REAR measurements. In such cases, prediction of the in situ REAR from real ear coupler difference (RECD) values has long been advocated as a viable and accurate alternative. Although rarely used with adult listeners, this method represents the standard, clinically-accepted protocol for fitting hearing aids in younger children and infants (e.g., Moodie, Seewald, & Sinclair, 1994; Mueller, 2005; Tharpe, Sladen, Huta, & Rothpletz, 2001). The RECD is the dB difference, across frequency, between the SPL measured in the patient's real ear for a specified sound coupling (i.e., foam insert or earmold/tubing) relative to the SPL measured in a testbox coupler. In average adult patients with normal middle ear function, RECDs obtained from foam inserts are relatively consistent and thus average RECD values measured with this coupling are not highly variable (e.g., Benter & Pavlovic, 1989; Sinclair, Beauchaine, Moodie, Feigin, Seewald, & Stelmachowicz, 1996; Munro & Hatton, 2000; Munro & Millward, 2006). Earmold venting and tubing length, however, can affect RECDs values (e.g., Gustafson, Pittman & Fanning, 2013). For example, venting can cause leakage of amplified sounds that results in negative low frequency RECD values (e.g., Galster, McCreery, & Irey, 2014). The tubing length also can affect the RECD such that with increasing tubing length, there can be a 7-8 dB decrease at 4000 Hz (e.g., Gustafson et al., 2013). Given that the effects of earmold coupling (i.e., vent size and tubing length) are known, the average RECD values (based on foam insert coupling) can be corrected to better account for individual differences in earmold coupling. Such correction values readily are available (e.g., Dillon, 2012; Scollie, Seewald, & Jenstad, 1998; Vonlanthen, 1996). On the other hand, the effects of coupling differences with earmolds can be accounted for by actually measuring the RECD using the patient's own custom earmold (e.g., Hoover, Stelmachowicz, & Lewis, 2000; Munro & Buttfield, 2005). Indeed, research comparing measured REARs to derived REARs using RECDs with the patient's custom earmolds has shown good agreement (± 5 dB) and are appropriate for clinic use (e.g., Bagatto, Scollie, Seewald, Moodie, & Hoover, 2002; Galster et al., 2014; Moodie et al., 1994; Munro & Hatton, 2000). Thus, RECD-based, hearing-aid verification has been proven effective and a clinically

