EXP-open or EXP-closed Group Fittings. The participants in these groups will **not** be present during the fitting. These fittings will follow the same procedures as the testbox fittings in Study 1.

The only difference is the correction factors used will be determined from Study 2, and the measured RECD will be corrected as determined from study 2.

Two-Day Follow-Up Phone Call. All participants will receive a 2-day follow-up phone call after the hearing-aid fitting (either in situ fitting for SoC groups, or after delivery of hearing aid is confirmed with the delivery receipt for EXP groups) using the same telephone script (Appendix) as in Study 1.

Session 3-One-Month Post-Fitting. Session 3 procedures will be the same as in Session 3 in Study 1. In short, the self-report outcomes and exit interview will be assessed based on the patient experience of the replacement fittings. In addition, in situ REARs will be obtained from all groups using the current programming from the replacement aids. These in situ REARs will allow within and between group comparisons regarding the hearing-aid function and determine the accuracy of the experimental fittings relative to the SoC fittings. The repeat in situ REAR measurements in the SoC group (i.e., Sessions 2 and 3) will serve to assess the inherent variability with in situ REAR measurements and will facilitate interpretation of REAR data when comparing the accuracy of the in situ and derived REARs in the experimental groups.

Adverse Events

Given the study population (healthy Veterans with no more than a moderate sensorineural hearing loss), who are obtaining replacement hearing aids (Study 1 and 3), there are very few unexpected or anticipated serious events. In rare cases, ear injury during an earmold impression procedure could occur (Study 1 only), or occasional mild discomfort during probe microphone measurements (Studies 1, 2, and 3). Otherwise, participants may experience boredom or frustration with the taking a hearing test, listening to speech, or completing study questionnaires. All adverse events will be reported per Durham VAMC requirements. All Serious, Unanticipated and Related adverse events will be reported to IRB within 5 business days of hearing of the event. All other adverse events will be reported at continuing review.

Costs and/or Payments to Subjects

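### Hypothesis 2 is met once any correction factors exist, and the Study 2 analysis has no out-of-sample measure of how well they predict the real-ear response, so Aim 2 cannot return a negative answer

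*Combined protocol and SAP*

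**What the plan says.** Under Purpose, Specific Aim 2, the whole of Hypothesis 2 is "Correction factors will be developed to account for RECD coupler-based fittings with open canals". Its neighbour, Hypothesis 1a, makes a claim that data could contradict: "RECD coupler-based fittings will accurately meet prescriptive targets and expected aided audibility for ITE and traditional BTE styles".

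The Study 2 Data Analysis paragraph says "The data from this study will not be analyzed in the usual manner as the purpose of this study is to develop correction factors". It calculates gain deviations by frequency for each ear, then fits linear and nonlinear models "with the goal of developing a best fit model of the relationship between physical vent size and the frequency specific change in gain". The only further provision is an adjustment, if needed, "to account for cases when the model correction would erroneously lead to negative gain".

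The Study 2 Power Analysis sets 96 participants, each with 12 fittings in one ear. It justifies the 96 by coverage of RECDs and slit-leak variation, not by a precision or error target.

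For the experimental groups in Study 3, the fitting procedure follows the Study 1 testbox procedure: "The only difference is the correction factors used will be determined from Study 2". No condition is attached to that use.

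**The concern.** Two features combine.

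- **The hypothesis has no content that data could contradict.** Some model always fits best, however poorly, so completing the analysis is enough to confirm Hypothesis 2. A development aim need not be a significance test, but it needs a stated standard of adequacy.
- **The only stated criterion is goodness of fit.** The plan does not say that fit is to be judged on ears the model has not seen. A model chosen from several linear and nonlinear candidates, and assessed on the same ears, gives an optimistic picture. Repeated fittings add to this. If single fittings were held out, 11 others from the same ear canal would remain in the fitting data.

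At stake is what Aim 2 can conclude. The factors are meant for new patients, and the experimental groups in Study 3 are the first to have aids fitted with them. A reader of the Study 2 report would have no planned figure for the error to expect in a new ear.

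**Working it through.** **Reproducing the plan's own figure.** Study 2 targets 96 evaluable participants and adds 10%: 96 × 1.10 = 105.6, which rounds up to the stated 106. (Dividing by 0.90 gives 107, a trivial difference.) No alpha, power, effect size or precision target is given for Study 2, so there is nothing further to recompute.

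**Does any other step test the factors before Study 3 uses them?**

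- *Testbox criterion (Study 1, Session 2, reused for the experimental groups).* Output must lie within ±3 dB of target in a sealed coupler, and the vent correction is applied afterwards. The Study 3 text also speaks of correcting the measured RECD. Whichever order is meant, the check involves no real ear, so it cannot show whether the corrected value predicts one.
- *85 dB sweep.* This compares maximum output with predicted loudness limits.
- *Two-day telephone call.* This asks about comfort, sound quality and problems.
- *Session 3.* In situ REARs are measured in all groups. This does test accuracy, but in Study 3, one month after fitting.

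None of these is a Study 2 result.

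**Why a small average error is not enough (illustration).** Assume the prediction error at one frequency is normal with mean 0 and standard deviation SD. The share of ears outside ±5 dB is 2 × [1 − Φ(5/SD)].

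| Assumed SD (dB) | Share outside ±5 dB |
|---|---|
| 2.5 | 4.6% |
| 4 | 21.1% |
| 5 | 31.7% |
| 6 | 40.5% |

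At SD 5 dB the standard error of the mean error over 96 ears is 5/√96 = 0.51 dB. The mean would look precise and close to zero while nearly a third of ears were poorly predicted. A bias makes this worse. With a 3 dB bias and SD 5 dB, the share inside is Φ(2/5) − Φ(−8/5) = 0.60, against 0.68 without bias.

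The SDs and the bias are assumptions. The ±5 dB is taken from Background section 1c only to put numbers in.

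**Can the planned sample support a criterion?** Each ear has 3 manufacturers × 2 styles = 6 fittings per coupling, so all 96 ears inform both open and closed domes. Take one outcome per ear (within tolerance or not), one frequency and one coupling. Treat the cross-validated outcomes as independent, and use exact binomial calculations with an example floor of 80%:

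- *All 96 ears, one-sided 5% test.* Pass with at least 84/96. The false-pass probability is 0.038 at a true share of 0.80, and the pass probability is 0.84 at a true share of 0.90.
- *All 96 ears, lower limit of the two-sided 95% interval at least 80%.* Pass with at least 85/96 (lower limit 80.4%). The pass probability is 0.75 at a true share of 0.90.
- *All 96 ears, observed share at least 90%.* This needs 87/96, because 86/96 is 89.6%. The pass probability is 0.50 at a true share of 0.90.
- *Hold-out of 32 ears, one-sided 5% test.* Pass with at least 30/32. The false-pass probability is 0.032 at 0.80, and the pass probability is only 0.37 at 0.90.

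Cross-validation over all ears is therefore workable at the planned size, and a one-off hold-out of 32 is weak. How the rule is worded matters. Requiring every frequency and both couplings to pass together would lower these probabilities further.

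**The case against.** The strongest reply is that Study 2 is openly a development study, and that accuracy is tested where it belongs, in Study 3 under Hypothesis 3a. It also has practical safeguards: the 85 dB check, the follow-up call and access to the current aids. This stands as a reason for modest priority. It does not give Aim 2 a result that could be negative, and none of the safeguards measures the factors' error.

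A second reply is that the ±5 dB figure is borrowed. This stands. In section 1c the sentence saying that research "has shown good agreement (± 5 dB) and are appropriate for clinic use" concerns RECDs measured with the patient's own custom earmolds. Study 2 concerns non-custom domes, and the same section warns of low-frequency leakage through vents. Nor does the text say whether ±5 dB describes a mean difference or a limit for individual ears. It can be a starting reference and no more.

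A reader might go on to infer that a failure in Study 3 could not be traced to the factors as opposed to the mailed delivery. The documents do not support that. Study 3, Session 3 plans in situ REARs in all groups, with repeat SoC measurements to gauge variability when in situ and derived REARs are compared in the experimental groups. Self-report outcomes and the exit interview are collected separately.

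A reader might also infer that poor factors would come to light only after all 44 experimental participants (2 × 22) had received aids. That is not shown either. Each participant's in situ check follows one month after fitting, and nothing says that all aids go out before the first such visit. The 44 is also the attrition-inflated count; the evaluable target is 2 × 19 = 38.

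**Conclusion.** The concern holds for Aim 2 itself. Hypothesis 2 cannot be contradicted by data, and the Study 2 analysis plans no out-of-sample measure of how well the corrected RECD predicts the in situ response. This rests on the text and needs no assumption.

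The practical size is unknown. Between about 5% and 40% of ears could miss ±5 dB at a given frequency for assumed SDs of 2.5 to 6 dB. Those figures depend on normal, unbiased errors and on a tolerance the protocol has not adopted for domes, and they do not show that the factors will be poor. The pass probabilities rest on independent outcomes per ear and on example shares.

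This is a recommended improvement at low cost. It does not undermine the Study 3 comparison.

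**What to change.** **Hypothesis 2.** Restate it as a prediction-accuracy claim: in ears not used for fitting, the REAR predicted with the corrected RECD lies within a stated tolerance of the measured in situ REAR in at least a stated share of ears.

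**Study 2 Data Analysis.**

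- Choose among the linear and nonlinear models, and report the error of the chosen one, by cross-validation that leaves out whole participants, with all 12 fittings of an ear removed together. Repeat the model choice within each fold.
- Report, by frequency and separately for open and closed domes, the mean error, the SD and the share of ears within tolerance, with 95% confidence intervals.
- Before analysis, the sponsor fixes and justifies the tolerance, the required share, whether that share applies to the observed value or to a confidence limit, the set of frequencies, and how repeated fittings per ear are combined. The ±5 dB in Background 1c is a starting reference only.
- If the criterion is missed, report Aim 2 as not met. Refitting on the same ears may follow, but it does not reset that result. Otherwise the aim again becomes one that cannot fail.

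**Study 3.** Whether experimental fittings should depend on the Study 2 result is for the investigators to decide and state.

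**Cost.** Changed wording in Aim 2 and in the Study 2 analysis, and one extra analysis. No new visits are needed, because Study 2 already measures in situ responses with both couplings. The drawback is that the sponsor must commit to a criterion in advance and may miss it.
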